### **3. Materials and methods**

#### *3.1. Participants and Study Design*

This study was planned as a multicenter, randomized, double-blind, and crossover. Approval was obtained from the Erciyes University Clinical Research Ethics Committee for the study (Decision No: 2018/259, Date: 09.05.2018). Twenty healthy adults (10 men, 10 women) between the ages of 19-35, with normal body weight (BMI 18.5-25 kg /m^2) were included in the study. Exclusion criteria were applying an energy-restricted diet in the last three months, having a change in body weight >5 kg in the last three months, having a chronic disease such as diabetes and hypertension, or using a drug that affects the metabolism, having fasting glucose >100 mg/dl, smoking, exercising heavily, having chewing/swallowing difficulties or sensitivity/allergies to any food to be used in the study, vegans, pregnant and lactating women, and skipping breakfast meals. Participants were selected from among Erciyes University students and staff in accordance with the inclusion criteria. Before the participants were included in the study, they were informed about the study in accordance with the Declaration of Helsinki, and volunteers were asked to read and sign the informed consent form.

The physical activity levels of the participants were evaluated simultaneously with dietary assessment by the International Physical Activity Questionnaire (IPAQ) short form at the beginning of the study and on each test day. Their dietary intakes were also assessed by the a-24-hour dietary recall using a photographic atlas of food portion sizes to quantify the data. Diet composition was analysed by the BeBiS Nutrition Information System software version 8.2. Furthermore, body weight and height of participants were obtained at the beginning of the study, and BMI was calculated. Waist and hip circumference were measured using a non-elastic tape with the participants standing, with the face directed towards, shoulders relaxed, and the tape was positioned at a level parallel to the floor. The eating behaviors of all participants were also evaluated using the Dutch Eating Behavior Questionnaire before starting the study. Since the total score obtained from this questionnaire >3.5 is considered as restrictive eating behavior (15), these individuals were not included in the study.

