### 3.5. Postprandial Appetite and Glucose Assessment

A visual analog scale (VAS) was used to assess appetite before breakfast and at 15, 30, 60, 90, 120, 150, and 180 minutes after breakfast (23). Furthermore, the separate VAS components such as hunger, fullness, desire to eat, and prospective food consumption were combined to produce an additional measure termed ‘composite appetite score’. This validated average appetite score was calculated for each time point using the following equation:  $[(\text{hunger} + \text{desire to eat} + \text{prospective food consumption} + (100 - \text{fullness}))]/4$  (24).

For the postprandial glucose assessment, blood glucose measurements were made using a finger-tip glucometer (Accu-Check, Roche Diagnostics) at 0, 15, 30, 45, 60, 90, and 120 minutes.

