### 3.6. Ad libitum Lunch

At the end of three hours, the ad libitum lunch was served to the participants as a buffet-style, and the energy and macronutrient intakes in this meal were determined. All foods (meatballs, tuna, sauce pasta, yogurt, salad, white bread, apple, banana, yogurt drink, fruit juice, and water) were weighed using a calibrated kitchen scale with an accuracy of  $\pm 1\text{g}$  before being served. At lunch, the participants were asked to consume the foods they wanted and continue eating until they felt completely full. After the participants completed their consumption, the remaining amounts were reweighed and the difference with the initial amounts was accepted as the amount consumed. Energy and macronutrient values were calculated using The National Food Composition Database (TurKomp), and manufacturer labelling.

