## 4. Statistical Analysis Plan

### 4.1. Sample size

A power-based sample size calculation based on previous research from Bo et al. (25) revealed that 16 participants were needed to provide 80% power to detect 5% difference between groups in primary outcomes. To allow discontinuation during the study, 20 participants (considering 25% losses) were recruited.

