### 4.2. Data analysis

Statistical analysis was performed using the SPSS Statistics (version 22.0) software. Data were expressed as the mean  $\pm$  SD unless otherwise indicated. Normality was assessed using the histogram and normal Q-Q plots, and also Shapiro-Wilk test. Postprandial appetite and glucose responses were quantified as incremental area under the curve (iAUC) calculated according to the trapezoidal rule. One-way analysis of variance (ANOVA) for repeated measures was applied to determine statistical differences between groups. For all statistical analyses, p values less than 0.05 were considered to have statistical significance.

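### The one-way repeated-measures ANOVA would, as normally run, discard every visit of a participant who misses one; an all-visits mixed model would keep them (a conditional loss of precision, not an error)

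*Combined protocol and SAP*

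**What the plan says.** Section 3.1 describes the design: "This study was planned as a multicenter, randomized, double-blind, and crossover". Each participant eats four breads on four separate days. Section 4.2 is the whole analysis plan. It reduces glucose and appetite to one number per visit ("Postprandial appetite and glucose responses were quantified as incremental area under the curve (iAUC) calculated according to the trapezoidal rule") and then names one model: "One-way analysis of variance (ANOVA) for repeated measures was applied". Bread is the only factor. For lunch, section 3.6 says that "the energy and macronutrient intakes in this meal were determined", and no other model is named for those outcomes.

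Section 4.1 gives 16 as the number needed for 80% power at a 5% difference, and adds: "To allow discontinuation during the study, 20 participants (considering 25% losses) were recruited". No section gives a rule for a missed visit, and none says how the bread orders were allocated.

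**The concern.** A classical one-way repeated-measures ANOVA works on complete rows. A participant with three good visits and one missing contributes nothing, although those three visits still carry within-person information on the breads attended. The plan foresees losses and handles them only by recruiting more people, not by keeping what the incomplete people have provided. With 20 participants, each discarded set of visits is a noticeable share of the data. At stake is the width of the confidence intervals for the bread comparisons, including barley or oat against whole-wheat bread, on which the fibre-independent objective in section 2 rests.

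**Working it through.** **Inputs from the documents.** Four breads per person; 20 recruited; 16 needed for 80% power; 25% losses; significance level 0.05 (sections 3.1, 4.1, 4.2). **Assumptions.** Two-sided test; common within-person variance σ² for all breads; missed breads fall at random; bread-only model. The documents give no missed-visit rate.

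**The plan's own figure.** The 16 cannot be reproduced, because no SD is given. It can be back-solved. For a paired t test, 80% power at 16 needs difference/SD of differences = 0.749, so a 5% difference implies an SD of differences of 5/0.749 = 6.7%. The inflation to 20 matches 16 × 1.25 = 20, which leaves room for 4 losses. Read instead as 25% of the 20 recruited, it means 5 losses and 15 completers.

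**Information kept from a partial participant.** A person with m of 4 visits contributes, averaged over which breads are missing, (m − 1)/3 of a complete person's within-person information:
- three visits: 2/3
- two visits: 1/3
- one visit: 0

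If k of 20 people are partial, the effective number is n_eff = (20 − k) + k(m − 1)/3, against 20 − k for completers only. The variance of a difference between two breads is 2σ²/n_eff.

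**Power.** Noncentral t with noncentrality δ√(n_eff/2), where δ is the difference in within-person SDs. Degrees of freedom are 3(n − 1) for n completers, or visits − 20 − 3 for all visits. Setting power to 80% at 16 completers (45 df) gives δ = 1.012. With 20 complete participants (57 df) power is then 88%.

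| Incomplete of 20 | Visits missed by each | n_eff, completers / all visits | df | SE ratio | Power, completers / all visits |
|---|---|---|---|---|---|
| 0 | – | 20 / 20 | 57 / 57 | 1 | 88% / 88% |
| 4 | 1 | 16 / 18.67 | 45 / 53 | √(16/18.67) = 0.926 | 80% / 86% |
| 4 | 2 | 16 / 17.33 | 45 / 49 | √(16/17.33) = 0.961 | 80% / 83% |
| 4 | 3 | 16 / 16 | 45 / 45 | 1 | 80% / 80% |
| 5 | 1 | 15 / 18.33 | 42 / 52 | √(15/18.33) = 0.905 | 77% / 85% |
| 5 | 2 | 15 / 16.67 | 42 / 47 | √(15/16.67) = 0.949 | 77% / 82% |

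With fewer people affected the gain is smaller: if 1 or 2 of 20 miss one visit, the SE is 1.7% or 3.5% lower.

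**Cross-checks.** Drawing the missed breads at random, instead of using the average, gives SE reductions of 7.3% and 3.8% for four people missing one or two visits, against 7.4% and 3.9% above. A separate simulation had 5 of 20 leaving at random after visit 1, 2 or 3, with no visit effect, balanced order and a largest bread difference of 1.2 within-person SD. The mean SE was 0.363 for completers and 0.345 for all visits (0.345/0.363 = 0.95), and power was 0.75 and 0.80.

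**Validity.** With no bread effect and a visit effect spanning 1 within-person SD, the named ANOVA rejected in 2% to 5% of simulated trials at the nominal 5% level.

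**The case against.** The strongest reply is that the plan contains no error. The ANOVA compares breads within person and is valid for a randomised crossover with complete data. The losses are budgeted: after four complete losses, completers alone still meet the 80% target. No section reports a missed visit, and section 4.1 speaks of discontinuation, which could mean people who leave after one visit and would then add almost nothing. All of this stands, and it is why the point is optional. What remains is that the plan does not say what becomes of completed visits, and that keeping them helps whenever a partial participant has two or three.

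A second reply is that the simple mixed model brings its own risk, because it assumes equal variance across breads. That also stands. If white bread had 1.5 times the residual SD of the others, pooled-error pairwise tests at nominal 5% would run at about 2.6% for barley versus whole-wheat and 7.5% to 7.9% for white-bread contrasts. The covariance check under the fix is there for this reason. The degrees of freedom that a flexible covariance costs were not quantified.

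A reader might go further and call the absence of period and fasting terms a defect. The documents do not support that:
- **Period.** They show no visit effect and do not say whether bread order was balanced. With no visit effect, a period term widens the confidence interval by about 0.1% if order was balanced and about 3% if it was unrestricted.
- **Fasting values.** Fasting glucose and pre-breakfast appetite are measured (section 3.5), and an incremental area conventionally subtracts them. Their further value as covariates depends on a correlation that the documents do not give; the interval is slightly wider at a within-person correlation of 0 or 0.1.

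**Conclusion.** The point holds as a conditional loss of precision. On the plan's own power calibration, keeping completed visits is worth about 3 to 6 power points if 4 of 20 are partial, and about 4 to 8 points if 5 of 20 are. It is worth essentially nothing if the partial participants completed only one visit, and nothing if everyone completed all four.

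The figures rest on a bread-only, common-variance model with visits missed at random. They are not the net gain of a larger model with period, fasting or flexible-covariance terms, which was not computed.

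A reader might infer that the trial is underpowered or that its type I error is inflated. Neither follows. Complete-case power stays at 80% after four losses and falls only to 77% after five, and the simulated rejection rates under the null do not exceed the nominal level.

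**What to change.** State a missed-visit rule: all completed visits are analysed. Replace the ANOVA with a linear mixed model for each outcome (SPSS MIXED, Satterthwaite degrees of freedom), with bread fixed and participant random. Check the result with a covariance that may differ across breads, or with the sphericity-corrected ANOVA on completers.

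State how bread orders were allocated. If they were balanced, a pre-specified period term is a reasonable addition. If not, weigh its possible cost of about 3% in interval width. A fasting covariate is optional for glucose and appetite. Choose any such terms in advance, not by their p-values.

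The change needs the same data and the same software. Its price is the reliance on equal variances in the simple model, or some degrees of freedom in the flexible one. The plan is written in the past tense; if outcomes have already been examined, keep the stated ANOVA as the main analysis and report the mixed model beside it as a labelled sensitivity analysis.
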